### **2.3.3 Medical History**

Any condition entered on the *Medical History* CRF will be coded using the MedDRA dictionary. These will be summarized by system organ class (SOC) and preferred term (PT) of the MedDRA dictionary for the Enrolled Set, the Responder Set, the Nonresponder Set and by treatment group for the Safety Set. Summaries for cardiovascular medical history as collected on *Cardiovascular Medical History* CRF will be provided as well.

*Ankylosing Spondylitis disease background* including time (years) since axial symptom onset, time (years) since diagnosis of ankylosing spondylitis, TNF-alpha exposure, inhibitor treatment and response status along with history of extra-axial involvement, will be summarized at Screening Visit 1 for the Enrolled Set, the Responder Set, and by treatment group for the Full Analysis Set and Safety Set.

*Smoking history* and *alcohol history* as collected at baseline, will be summarized for the Enrolled Set, the Responder Set, and by treatment group for the Full Analysis Set and Safety Set.

## **2.4 Treatments (study treatment, rescue medication, concomitant therapies, compliance)**

### **2.4.1 Study treatment / compliance**

#### **Study Treatment**

The summaries by treatment group will be performed by the actual treatment received (as follows) for every visit until Week 16.

Treatment groups in Treatment Period 1:

- Secukinumab 150 mg

In Treatment Period 2, the summaries by treatment group will be performed by the actual treatment received (as follows) for every visit up to Week 52, including patients who switched at Weeks 16.

Treatment groups in Treatment Period 2:

- Secukinumab 150 mg - 300 mg (IR)
- Secukinumab 150 mg - 150 mg (IR)
- Secukinumab 150 mg – 150 mg (R)

where, R: Responders and IR: Inadequate Responders

Treatment groups in entire treatment period:

- Secukinumab 150 mg

- Secukinumab 300 mg

### **Duration of exposure**

The duration of exposure (in days) will be summarized by means of descriptive statistics for the Enrolled Set, the Responder Set, and each treatment group for the Safety Set. In addition, the number of subjects with exposure of at least certain time thresholds will be displayed (e.g. any exposure,  $\geq 1$  week,  $\geq 2$  weeks,  $\geq 3$  weeks,  $\geq 4$  weeks,  $\geq 8$  weeks, etc.).

For Treatment Period 1, the end date for the calculation of duration of exposure will be the earlier of:

- Date of last injection in Treatment Period 1 + 84 days, and
- Date of first injection in Treatment Period 2

For Treatment Period 2, the end date for the calculation of duration of exposure will be the date of last injection in Treatment Period 2 + 84 days.

For entire treatment period, the end date for the calculation of duration of exposure will be the date of last injection + 84 days.

For patients with death as an event, end date for calculation of duration of exposure will be the date of death if it is earlier than the date of last injection + 84 days.

Duration of exposure (years) = duration of exposure (days) / 365.25

Duration of exposure (100 patient years) = duration of exposure (years) / 100

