5.6 Study completion and discontinuation

5.6.1 Study completion and post-study treatment

The last scheduled administration of therapy will be at Visit 18/Week 48. A subject's study participation is completed once Visit 19/Week 52 has been completed. After this date, any SAEs that occur in the following 30 days must be reported. The investigator will also follow any AEs for which there is no outcome that can be reported at the final study visit. Pregnancies will be followed until the outcome of the pregnancy is known.

Information on the subject's completion or discontinuation of the study and the reason for discontinuation of the study will be recorded on the corresponding CRFs.

In any case, the investigator or site staff must contact the IRT system as soon as possible to record the subject's study completion (Week 52) and/or withdrawal from the trial.

The study as a whole will be completed once all enrolled patients have completed the study per the protocol and the clinical database has been locked. Recruitment into the study will be terminated by the sponsor once the targeted number of randomized patients has been met or is foreseen to be met with the patients already in screening. Patients who have been screened and have a screening visit recorded in the IRT system at the time that the planned enrollment number is met will be allowed to enter the trial and to be randomized if they are eligible.

Upon completion of study participation, patients will return to individual medical treatment, as determined by their treating physician.

The Investigator must provide follow-up medical care for all patients who are prematurely withdrawn from the study, or must refer them for appropriate ongoing care.

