Screening will be flexible in duration based on the time required to be evaluated for eligibility. Sufficient time is allowed for potential medication washout, in addition to all other assessments indicated in [Table 6-1](#). Upon the completion of screening and confirmation that all inclusion and none of the exclusion criteria have been met, the subject may begin the Baseline Visit.

Screening will consist of two consecutive visits. During Screening Visit 1 (SV1) and Screening Visit 2 (SV2), initial assessments will be performed as outlined in [Table 6-1](#).

Patients who may be eligible for Screening Visit 2 immediately following Screening Visit 1 should have at least one week in between these two screening visits.

Premature Discontinuation

For patients who discontinue study treatment prematurely for any reason after baseline, an End of Study Visit must be performed approximately four weeks after the last dose of study treatment. In accordance with SAE reporting guidelines, any SAEs reported in the 30 days after the End of Study Visit, regardless of causality, must be reported to Novartis within 24 hours of learning of its occurrence and recorded in the eCRF.

Documentation of attempts to contact the subject should be recorded in the source documentation.

Unscheduled visits

Patients may be seen at any time for an unscheduled visit, e.g., if they experience deterioration or AEs that in the opinion of the investigator/qualified site staff need intervention or repeat laboratory testing. The assessment(s) performed at an unscheduled visit must include at minimum: an assessment of concomitant medication and procedures/significant non-drug therapies, vital signs, and an AE/SAE assessment. Any additional assessments performed are at the investigator/qualified site staff's discretion. During an unscheduled visit, study treatment will not be administered.

Table 6-1 Assessment schedule

Period	SCR ¹		Treatment Period 1 (Open-Label)								Treatment Period 2 (Double-Blind or Open-Label)								Telemedicine/ telephone visit	Unscheduled	Notes		
	-13 to -3	-2 to BL	BL	1	2	3	4	8	12	16	20	24	28	32	36	40	44	48				52/Study Completion/ EOS ²	
Visit No	1	2	3	4	5	6	7	8	9	10	11	12	13	14	15	16	17	18	19				
Assessments																							
Obtain informed consent	X																						See section 10.2
Inclusion / exclusion criteria	X	X	X																				See sections 4.1 – 4.2
Demographics	X																						See section 6.3

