### On-treatment period

The period where the patients are exposed to the study treatment. For this study the treatment phase consists of 52 weeks.

[figure not shown]

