#### **5.4.5 Exposure-adjusted incidence rate and $100*(1-\alpha)\%$ confidence interval**

It will be assumed that for each of  $n$  subjects in a clinical trial the time  $t_j$  ( $j=1, \dots, n$ ) to the first occurrence of a certain event is observed, or if the event was not experienced, the (censored) time to the end of the observation period. The total exposure time will be the total number of days with an actual dose greater than zero summed up over all patients, and then divided by 365.25 days. Incidence rate will be calculated per 100 patient years.

The sequence of first occurrences of an event will be modeled to follow approximately a Poisson process with constant intensity  $\theta$ . The rate parameter  $\theta$  will be estimated as  $\lambda = D/T$ , where  $T = \sum t_j$ , ( $j=1, \dots, n$ ) and  $D$  is the number of subjects with at least one event. Conditionally on  $T$ , an exact  $100*(1 - \alpha)\%$  confidence interval for a Poisson variable with parameter  $\theta T$  and observed value  $D$  can be obtained based on (Garwood,1936), from which an exact  $100*(1 - \alpha)\%$  confidence interval for  $D/T$  will be derived as follows (Sahai and Anwer, 1993; Ulm, 1990):

Lower confidence limit:

$$L = \frac{0.5c_{\alpha/2, 2D}}{T} \text{ for } D > 0, 0 \text{ otherwise,}$$

Upper confidence limit :

$$U = \frac{0.5c_{1-\alpha/2, 2D+2}}{T}$$

where  $c_{\alpha, k}$  is the  $\alpha$  th quantile of the Chi-square distribution with  $k$  degrees of freedom.

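### SAP 2.4.1 counts exposure to 84 days after the last injection, about 56 days beyond routine collection of non-serious adverse events, and SAP 5.4.5 does not settle which time the adverse event rates use

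*SAP*

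**What the plan says.** **Exposure (SAP 2.4.1).** Treatment Period 2 exposure ends at "the date of last injection in Treatment Period 2 + 84 days". For the whole study, "the end date for the calculation of duration of exposure will be the date of last injection + 84 days". The only general cap is death. Period 1 has one more: it stops at "Date of first injection in Treatment Period 2" if that comes before 84 days after the last Period 1 injection. Exposure is then converted to years and to 100 patient-years.

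**Follow-up (protocol).** Section 5.6.1: "The last scheduled administration of therapy will be at Visit 18/Week 48", and participation ends with the Week 52 visit. For early stoppers, section 6 says that "an End of Study Visit must be performed approximately four weeks after the last dose of study treatment".

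**Event collection (protocol).** Section 7.1 has adverse events sought at study visits. New events beyond the observation period that are thought related go to source documents, and to the sponsor only if serious. Of the time after the Week 52 visit, section 5.6.1 says: "After this date, any SAEs that occur in the following 30 days must be reported". Under section 7.2.1.1, serious events later than that are reported only if a causal link is suspected.

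**Rates (SAP).** Section 2.8.1 uses an 84-day window for treatment-emergent events. It plans exposure-adjusted rates for the entire treatment period by dose, with patients who escalate shown in both dose groups. Section 5.4.5 describes total exposure as the days on which a dose above zero was given. It also sums, per patient, the time to first event or "the (censored) time to the end of the observation period". It does not mention 84 days or refer to section 2.4.1.

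**The concern.** The exposure rule credits each patient with time in which the protocol has no routine means of recording a non-serious event. Published patient-years would then describe follow-up that did not take place. If the same time is the denominator of the exposure-adjusted rates, it enters without a matching chance of an event in the numerator, and the rates come out too low.

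The rule is also uneven within Period 1. A non-responder who leaves at Week 16 is credited with more open-label exposure than a patient who continues, because only the continuing patient's tail is cut.

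**Working it through.** **The plan's own numbers.** Sample size: 1.96² × (0.2×0.8 + 0.1×0.9) / 0.10² = 96.04, rounded up to 97 per arm, as stated. Disposition: 270 × 0.9 = 243 reach Week 16. Of these 24.3 are responders, 194.4 are inadequate responders (97.2 per arm) and 24.3 are non-responders. Another 27 drop out in Period 1.

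**The gap.** With visits on schedule, 84 − 28 = 56 days. For serious events, collection runs to about 28 + 30 = 58 days after the last injection, so the gap is 26 days (26/308 = 8.4%; 26/420 = 6.2%), although suspected-related serious events are still reportable in it.

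**Per patient** (day 0 = first dose; Week 12 = day 84, Week 16 = 112, Week 48 = 336, Week 52 = 364):

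| Case | Counted days | Days to last visit | Uncovered share |
|---|---|---|---|
| Period 2 completer, either arm | 224 + 84 = 308 | 252 | 56/308 = 18.2% |
| Entire period, 150 mg throughout | 336 + 84 = 420 | 364 | 56/420 = 13.3% |
| Week 16 non-responder | 84 + 84 = 168 | 112 | 56/168 = 33.3% |
| Period 1 of a patient who continues | 112 (cut) | 112 | 0 |

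**Pooled entire-period dose groups, if 2.4.1 is the denominator.** Assumptions: Period 1 dropouts have their last dose at Week 4 (112 days counted, 56 observed), nobody drops out in Period 2, and escalated patients' 150 mg time ends at Week 16.

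- 150 mg counted: 121.5×420 + 97.2×112 + 24.3×168 + 27×112 = 69,023 days
- 150 mg observed: 121.5×364 + 97.2×112 + 24.3×112 + 27×56 = 59,346 days; uncovered 14.0%
- 300 mg counted: 97.2×308 = 29,938 days; observed 97.2×252 = 24,494 days; uncovered 18.2%
- Ratio of 300 mg to 150 mg rates when true rates are equal: 0.818/0.860 = 0.95

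**First-event rates.** Section 5.4.5 stops a patient's time at the first event, so a patient with an event adds no tail. With constant hazard λ and observed time o, p = 1 − exp(−λo). Expected events are Σp and counted time is Σ[p/λ + (1 − p)×56], without the 56-day term for the 150 mg time of escalated patients.

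| True rate per 100 patient-years | 150 mg too low by | 300 mg too low by | Ratio |
|---|---|---|---|
| 1 | 14.0% | 18.1% | 0.952 |
| 20 | 13.2% (17.4 reported) | 17.2% (16.6 reported) | 0.954 |
| 100 | 10.5% | 13.4% | 0.968 |
| 200 | 8.3% | 9.3% | 0.989 |

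**Does the direction hold?** The 300 mg group has the larger uncovered share in nine of ten disposition scenarios tried. It reverses (21.2% for 150 mg, 18.2% for 300 mg) with 30% Period 1 dropout, 30% non-responders and no responders. It also reverses if escalated patients' 150 mg time runs on to 84 days after their Week 12 dose while later events count towards 300 mg: the 150 mg total becomes 69,023 + 97.2×56 = 74,466 days, of which 20.3% is uncovered.

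**The case against.** The strongest objection is that section 5.4.5 governs the rates and does not use the 84-day rule. If its observation period ends at the last visit, this bias does not arise. That objection stands: the link from 2.4.1 to the rates is inference. It is a reasonable inference, since 2.4.1 converts exposure to 100 patient-years, the unit of the rates, and defines an entire-period duration, the period for which the rates are planned. But section 5.4.5 does not provide a usable alternative. Days with a dose above zero, taken literally, come to 16 for a completer (7 injection days in Period 1 and 9 in Period 2). The end of the observation period is not defined.

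A reader might infer that the plan favours 300 mg. The documents do not establish this. It needs 2.4.1 as the denominator and a cut of escalated patients' 150 mg time at Week 16, which the SAP does not state for the entire period. Nor is the randomised comparison distorted: both Period 2 arms carry the same 56/308, and section 2.8.1 plans crude incidence for each period. The pooled 150 mg group also holds all open-label time, so it is not a randomised contrast.

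A post-dose exposure convention is not wrong in itself. The protocol requires contraception for 16 weeks after stopping. The SAP's on-treatment definition ("For this study the treatment phase consists of 52 weeks") describes the length of treatment and is only weak evidence of a contradiction.

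Finally, shortening the event window in 2.8.1 could drop suspected-related serious events reported between about day 59 and day 84 after the last dose. That also stands, and the fix leaves the window alone.

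**Conclusion.** The mismatch is real. SAP 2.4.1 overstates patient-years by counting about 56 days per on-schedule patient without routine collection of non-serious events: 18%, 13% or 33% of counted time, depending on the patient's path. The 56 days are not a maximum. A patient lost just after an injection can have up to 84, and one who misses late doses but attends Week 52 has fewer. The end of non-serious collection is inferred from the visit schedule and protocol sections 5.6.1 and 7.1; no sentence states it outright.

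Understatement of the exposure-adjusted rates is conditional on 2.4.1 supplying the denominator, and is smaller for common events. The dose-group figures (about 14% and 18%, ratio about 0.95) rest further on the planned dispositions, the assumed Week 4 last dose for dropouts and the Week 16 cut. Whichever reading is taken, the SAP holds incompatible denominators for a reported safety result and needs one.

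**What to change.** - **SAP 2.4.1:** end exposure at the earliest of last injection + 84 days, last study visit and death, for Period 1, Period 2 and the entire period. Keep the existing cut at the first Period 2 injection for Period 1.
- **Escalated patients:** state that their 150 mg time ends at the first 300 mg injection.
- **SAP 5.4.5:** replace the wording about days with a dose above zero, and make the date above the single censoring date. For rates of serious events, use last visit + 30 days, limited to last injection + 84 days, and count only serious events up to that date.
- **SAP 2.8.1:** keep the 84-day treatment-emergent window for crude tables, so that no recorded event is lost.

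This needs a few clauses and some reprogramming, and no new data. Stated patient-years fall by about 13–18% (14% for pooled 150 mg and 18% for 300 mg on the planned numbers), and any rates that were to use the 2.4.1 time will look slightly less favourable. The document history dates the latest SAP revision after database lock, so the change should be recorded as a post-lock one.

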### **Compliance**

Compliance will be calculated based on documented study drug administrations and syringe counts and displayed by treatment group. It is calculated as follows:

Compliance (%) =  $100 * (\text{total no. of injections administered}) / (\text{no. of injections prescribed})$ .  
Compliance is expected to be 100%, unless temporary interruption is needed for safety reasons.

The analyses of duration of exposure and compliance described above will be done for Treatment Period 1 and Treatment Period 2.

## **2.4.2 Prior, concomitant and post therapies**

### **Prior and concomitant therapies**

Prior medications are defined as treatments taken and stopped prior to first dose of study treatment. Any medication given at least once between the day of first dose of study treatment and the date of the last study visit will be a concomitant medication, including those which were started pre-baseline and continued into the period where study treatment is administered. Summaries will be presented for the Enrolled Set, the Responder Set, and each treatment group for the Safety Set.

Medications will be presented in alphabetical order, by Anatomical Therapeutic Chemical (ATC) classification codes and grouped by anatomical main group. Tables will show the overall number and percentage of patients receiving at least one treatment of a particular ATC code and at least one treatment in a particular anatomical main group.

Significant prior and concomitant surgeries and procedures will be summarized by primary system organ class and MedDRA preferred term.

In addition, prior and concomitant medication data will be listed.

### **Rescue medication**

Rescue medication is not permitted during the study.

## **2.5 Analysis of the primary objective**

The primary objective is to estimate the difference between secukinumab 300 mg and secukinumab 150 mg treatment groups at Week 52 based on the proportion of subjects achieving ASDAS inactive disease (<1.3) status who did not meet ASDAS inactive disease criteria at Week 12 and Week 16.

### **2.5.1 Primary endpoint**

The primary efficacy variable is ASDAS inactive disease response (yes, no) and the primary analysis time point will be at Week 52.

The primary analysis will be done on Full Analysis Set (FAS).

### **2.5.2 Statistical hypothesis, model, and method of analysis**

Let  $\pi_j$  denote the probability of an ASDAS inactive disease at Week 52 for treatment group  $j$ ,  $j = 1, 2$ , where 1 and 2 correspond to secukinumab 150 mg and secukinumab 300 mg, respectively. Accordingly,  $\pi_j/(1 - \pi_j)$  is the odds for treatment group  $j$ ,  $j = 1, 2$ .

The primary efficacy variable will be analyzed at each time point until Week 52 using a logistic regression model with treatment, TNF-alpha inhibitor status (naive, inadequate responder), and Week 16 body weight as explanatory variables (Stokes, Davis, and Koch, 2012). The odds ratios and 95% confidence intervals for the odds ratios will be reported, based on the fitted model.

Number and percentages for ASDAS inactive disease response will also be reported for each treatment group, by TNF-alpha inhibitor status (naive, inadequate responder) by visit. A line plot for ASDAS inactive disease responders (%) from Week 16 to Week 52 will be presented. A similar line plot will be presented by TNF-alpha inhibitor status.

A line plot for ASDAS inactive disease responders (%) over entire treatment period (from Week 1 to Week 52) will be presented. A similar line plot will be presented by TNF-alpha inhibitor status.

Also, number and percentages for the patients with ASDAS inactive disease response in Treatment Period 1 who entered Treatment Period 2 will be provided based on the below criteria:

- Patients receiving 150mg (open label) (Enrolled Set)
- Patients receiving randomized 300mg and 150mg (Randomized Set)
- Patients who are responders (Responder Set)
- Patients who are nonresponders (Nonresponder Set)

In addition, the above analysis will be done by TNF-alpha inhibitor status and by visit.

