5.3 Treatment assignment and randomization

At Baseline through Week 12, the Interactive Response Technology (IRT) system will be used at each visit to dispense open-label treatment to enrolled patients. The system will specify unique medication numbers that will correspond to open-label treatment to be dispensed.

Responders: At Week 16 through Week 48, the IRT system will be used at each visit to dispense treatment and matching placebo to ASDAS-inactive disease responders. The system will specify unique medication numbers that will correspond to treatment to be dispensed.

Inadequate Responders: At Week 16, all ASDAS-inactive disease inadequate responder eligible patients will be randomized via IRT to one of the treatment groups in a ratio of 1:1 (secukinumab 300 mg or secukinumab 150 mg). The IRT system will assign a randomization number to the subject, which will be used to link the subject to a treatment group in the system and will specify unique medication numbers for treatment to be dispensed to the subject. The randomization number will not be communicated to any of the site staff. The IRT system will be used at each visit from Week 16 through Week 48 to dispense treatment.

The randomization numbers will be generated using the following procedure to ensure that treatment assignment is unbiased and concealed from patients and investigator staff. A subject randomization list will be produced by the IRT system provider using a validated system that automates the random assignment of subject numbers to randomization numbers. These randomization numbers are linked to the different treatment, which in turn are linked to medication numbers. A separate medication list will be produced by or under the responsibility of Novartis Drug Supply Management using a validated system that automates the random assignment of medication numbers to packs containing the investigational drug(s).

Randomization will be stratified by TNF-alpha inhibitor status (naive, inadequate responder). The stratification ensures balanced allocation of patients to treatment groups within the TNF-alpha inhibitor status strata.

The randomization scheme for patients will be reviewed and approved by a member of the Novartis Biometrics group.

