9.4.2 Statistical model, hypothesis, and method of analysis

Let π_j denote the probability of an ASDAS inactive disease at Week 52 for treatment group j , $j = 1, 2$, where 1 and 2 correspond to secukinumab 150 mg and secukinumab 300 mg, respectively. Accordingly, $\pi_j/(1 - \pi_j)$ is the odds for treatment group j , $j = 1, 2$.

The primary efficacy variable will be analyzed at each time point using a logistic regression model with treatment, TNF-alpha inhibitor status (naive, inadequate responder), and baseline body weight as explanatory variables (Stokes, Davis, and Koch, 2012). The odds ratios and 95% confidence intervals for the odds ratios will be reported, based on the fitted model.

The primary analysis of the primary efficacy variable will be based on the Full Analysis Set.

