9.4.4 Sensitivity analyses

A 95% confidence interval for the difference between the two treatment groups in the proportion of patients who have ASDAS inactive disease will be calculated using the normal approximation to the binomial distribution for the Full Analysis Set.

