### **2.5.3 Handling of missing values/censoring/discontinuations**

Patients who discontinue prematurely for any reason will be considered nonresponders from the time they discontinued through Week 52. Also, patients who do not have the required data to compute response (ASDAS components) at the specific time point will be classified as nonresponders.

In an additional analysis, missing data for ASDAS inactive disease response will be imputed using multiple imputation. Details for multiple imputation is presented in Appendix [Section 5.4](#).

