### **2.5.4 Supportive analyses**

A 95% confidence interval for the difference between the two treatment groups in the proportion of patients who have ASDAS inactive disease response will be calculated using the normal approximation to the binomial distribution for the Full Analysis Set.

The analysis will be performed at each time point in Treatment Period 2.

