## 3 Sample size calculation

The sample size was calculated based on the primary efficacy variable (i.e., ASDAS inactive disease response) at Week 52 for the Full Analysis Set. The expected ASDAS inactive disease response rates for secukinumab 300 mg and 150 mg treatment groups at Week 52 are 20% and 10%, respectively (corresponding to an odds ratio of 2.25), partly based on results from AIN457F2310 (MEASURE 2) study. With approximately 97 patients in each treatment group (total of 194 randomized patients), one will be able to estimate the difference between ASDAS inactive disease response rates of the two treatment groups at Week 52 with a “margin of error” (half-width of confidence interval) of 10% (corresponding to a standard error of 5%) for a two-sided 95% confidence interval (Julious and Patterson, 2004; nQuery Advisor 7.0).

It is expected that the study will need to enroll approximately 270 patients for the 16-week open-label period, to randomize approximately 194 patients who do not achieve ASDAS inactive disease status at Week 16 (inadequate responders). This assumes that 10% of the 270 enrolled patients will discontinue during the 16-week open-label period; among the remaining enrolled patients, it is assumed that approximately 10% will be responders, 80% will be inadequate responders, and 10% will be non-responders.

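### The objective and sample size concern the Week 52 difference in response rates, but the primary analysis reports an adjusted odds ratio, and the visible multiple-imputation steps give no difference with a confidence interval

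*SAP*

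**What the plan says.** **Objective.** SAP 2.5 sets out to "estimate the difference between secukinumab 300 mg and secukinumab 150 mg treatment groups at Week 52 based on the proportion of subjects" reaching ASDAS inactive disease. Protocol Table 2-1 agrees.

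**Sizing.** SAP 3 and Protocol 9.8 justify 97 per arm by the ability to "estimate the difference between ASDAS inactive disease response rates of the two treatment groups at Week 52" with a 95% interval half-width of 10 points, at expected rates of 20% and 10%. The odds ratio of 2.25 appears only in parentheses, without a precision target.

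**Primary analysis.** Protocol 9.4.2 states: "The primary efficacy variable will be analyzed at each time point using a logistic regression model with treatment", TNF-inhibitor status and body weight as explanatory variables. SAP 2.5.2 and 5.4.1 (headed as the primary analysis) use the same kind of model. The between-arm result is described as follows: "The odds ratios and 95% confidence intervals for the odds ratios will be reported, based on the fitted model". SAP 2.5.2 also reports numbers and percentages by arm.

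**The difference.** Protocol 9.4.4, among the sensitivity analyses, plans "A 95% confidence interval for the difference between the two treatment groups in the proportion of patients who have ASDAS inactive disease". SAP 2.5.4 repeats it as supportive, "calculated using the normal approximation to the binomial distribution for the Full Analysis Set", at each Treatment Period 2 time point. It is unadjusted. Protocol 5.3 says: "Randomization will be stratified by TNF-alpha inhibitor status (naive, inadequate responder").

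**Missing data.** SAP 2.5.3 counts patients who discontinue or lack ASDAS components as nonresponders and adds: "In an additional analysis, missing data for ASDAS inactive disease response will be imputed using multiple imputation". The steps in SAP 5.4.1 pool each arm's response rate on the logit scale and an odds ratio from GENMOD. SAP 5.4.4 is redacted. The document history says that confidence-interval text was added there, so its content is unknown.

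**The concern.** The study estimates; it states no hypothesis test, so the estimate and its interval are the result. The scale on which the question was posed and the trial sized is not the scale of the analysis called primary. An odds ratio conditional on covariates does not by itself give the difference in rates, and the planned 10-point precision says nothing about it.

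The practical consequence lies in the missing-data check. Under Protocol 5.6.2, patients who stop treatment leave the trial, so their Week 52 status is normally not observed. Non-response imputation is then a strong assumption, and multiple imputation is the visible alternative. If the between-arm comparison after imputation is made only on the odds ratio, the report will not show with an interval how far the quantity in the objective depends on that assumption.

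**Working it through.** **1. Reproduce the sizing.** Inputs from SAP 3: rates 0.20 and 0.10, half-width 0.10, two-sided 95%.

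n = 1.96² × (0.20×0.80 + 0.10×0.90) / 0.10² = 1.96² × 0.25 / 0.01 = 96.04, hence 97 per arm.

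At 97 per arm the half-width is 1.96 × √(0.25/97) = 9.95 points. The plan's figure is confirmed, and it is a calculation for the unadjusted difference.

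**2. The same data on both scales.** A crude odds ratio stands in for the adjusted one.

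- Difference: 10.0 points (0.05 to 19.95).
- SE of the log odds ratio: √[1/(97×0.16) + 1/(97×0.09)] = 0.423. The factor is exp(1.96×0.423) = 2.291, giving 2.25 (0.98 to 5.16).

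**3. Does the pre-specified interval work?** Enumerating all outcomes of Binomial(97, 0.20) and Binomial(97, 0.10):

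- coverage of the normal-approximation interval: 94.75%; mean half-width 9.87 points;
- the difference interval excludes 0 in 50.3% of trials and the crude odds-ratio interval excludes 1 in 48.0%;
- they disagree in 2.3%, always with only the difference excluding the null. Example: 20/97 against 10/97 gives 10.3 points (0.2 to 20.4) and an odds ratio of 2.26 (0.997 to 5.12).

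**4. Non-response imputation on the two scales.** The documents give no Treatment Period 2 missingness rate, so these fractions are assumed, with missingness ignorable. If fraction f is missing in an arm with true rate p, the analysed rate is p(1−f).

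| Missing, 300 mg / 150 mg | Analysed rates | Difference (points) | Odds ratio |
|---|---|---|---|
| none | 20% / 10% | 10.0 | 2.25 |
| 10% / 10% | 18% / 9% | 9.0 | 2.22 |
| 20% / 20% | 16% / 8% | 8.0 | 2.19 |
| 30% / 30% | 14% / 7% | 7.0 | 2.16 |
| 10% / 20% | 18% / 8% | 10.0 | 2.52 |
| 20% / 30% | 16% / 7% | 9.0 | 2.53 |
| 20% / 10% | 16% / 9% | 7.0 | 1.93 |
| 30% / 10% | 14% / 9% | 5.0 | 1.65 |

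With equal missingness the difference shrinks in proportion and the odds ratio barely moves. The interval also narrows: half-widths are 9.5, 9.1 and 8.6 points at 10%, 20% and 30%. With unequal missingness either scale can move more.

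**5. A pooled imputed difference.** In 4,000 simulated trials per rate, with 100 imputations by arm and equal missingness of 10%, 20% or 30%, the Rubin-pooled difference averaged 10.1, 10.0 and 9.9 points. Half-widths were 10.4, 11.1 and 11.8, and coverage was 94.8% to 95.1%. This imputation used no earlier-visit data. SAP 5.4.1 uses Weeks 16 to 52, which should narrow the intervals, so these half-widths are illustrative only.

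**6. What stratification gains.** Marginal rates are held at 20% and 10%. The assumed share of TNF inadequate responders is 20% or 40% (40% is the enrolment ceiling in Protocol 3.1), and their assumed odds ratio for response against naive patients is 1, 0.5, 0.25 or 0.1.

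- 20% share: half-width 9.95, 9.91, 9.84, 9.77 points.
- 40% share: half-width 9.95, 9.88, 9.73, 9.52 points.

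The gain is 0 to 0.43 points.

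**The case against.** **The difference is already planned.** SAP 2.5.4 sits inside the section on the primary objective, uses the Full Analysis Set, and applies the same approximation that reproduces the sizing. This stands. A reader might infer that the trial cannot answer its objective, or that 97 per arm is wrong. The documents support neither.

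**The shrinkage can be seen in planned output.** Rates by arm under non-response and pooled imputed rates by arm are both specified, so an imputed difference can be had by subtraction. This stands for the point estimate. What the visible text lacks is an interval for it, and redacted SAP 5.4.4 may or may not supply one.

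**The odds ratio is not generally insensitive.** It is tempting to infer that an odds ratio hardly reacts to non-response imputation. That holds only with equal missingness. At 10%/20% missing the odds ratio moves and the difference does not. The narrower statement survives: neither scale can vouch for the other.

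**Stratification changes little.** This stands. TNF status is already in the logistic model and response is tabulated by TNF status. The case for a stratified difference is consistency with the randomisation, with only a small gain in precision.

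**Promoting the difference now would be poor practice.** A reader might conclude that it should simply become the headline. The last SAP version is dated after database lock, both governing documents rank the difference below the logistic analysis, and step 3 shows that its interval excludes the null slightly more often. An undisclosed switch would be worse than the mismatch.

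**Conclusion.** The point holds as an alignment gap. Objective and sizing are on the difference scale. The analysis designated primary reports an adjusted odds ratio with no stated precision, and the difference is relegated to a crude supportive interval that does not use the TNF stratum. The visible imputation steps produce no difference with an interval; because of the redaction, the claim goes no further than the visible text.

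The main consequence concerns missing data. Under the assumed fractions, non-response imputation takes a true 10.0 points to anywhere from 10.0 down to 5.0, and the odds ratio from 2.25 to between 1.65 and 2.53, not in step with each other. Disagreement between the two intervals about the null is uncommon (2.3% at the planning rates, with a crude odds ratio in place of the adjusted one). All missingness and TNF-effect figures are assumptions.

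**What to change.** (a) In each imputed data set compute the Week 52 difference and its standard error, pool with Rubin's rules, and report the result with its 95% interval beside the non-response-imputed difference.

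(b) Add a Mantel-Haenszel difference stratified by TNF-inhibitor status, with a 95% interval, beside the crude one, and say that the precision gain is small. It remains usable if sparse responses trigger the exact logistic fallback in SAP 5.4.1.

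(c) Show the pre-specified crude difference next to the adjusted odds ratio, without re-designating it as primary. If the headline estimate is changed, disclose that this was done after lock.

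List (a), (b) and any change under (c) in SAP section 4 as post-lock; none should displace the pre-specified interval. The cost is a little extra programming on imputations already planned, plus the post-lock label. No new data are needed and the odds ratio is kept.
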